**6.3 Description of what research material, data, and information will be collected:**

Data will consist of written and audio information. Where possible, we will use item phrasing compatible with items from the Common Data Elements (CDEs) database. Data will be collected by RAs at each study site using REDCap, transferred and stored centrally in a REDCap database at Dartmouth College. We will collect information on recruited patients from several sources:

The electronic medical record (EMR): We will collect information on patient demographics (age, sex) and contacts (address, telephone, email), primary language spoken, the number and type of patient conditions, current treatment (e.g., medication), laboratory tests (e.g., urine albumin, blood pressure, HbA1c) number of clinic visits and contacts (e.g. phone calls, patient portal emails), and emergency room visits and hospitalizations. Baseline laboratory tests may be collected as much as 12 months prior to the T0 (baseline) timepoint, as certain tests (e.g., urine albumin and HbA1c) are routinely done on a yearly basis.

Patient reported: We will collect the following information from patients: demographics (age, sex, race, ethnicity, language spoken at home, and educational attainment), cognitive function (Six Item Screener scale), the Short Assessment of Health Literacy (SAHL-E), brief health literacy screen (BHLS), Patient Health Questionnaire(PHQ-8), Generalized Anxiety Disorder (GAD-7) the Patient Activation Measure – Short Form (PAM-SF), an assessment of mental and physical functioning (PROMIS), an assessment of Quality of life (EURO-QOL), an assessment of satisfaction with care (PSQ-18), clinic visit process (Interpersonal Process of Care), comprehensive diabetes stigma scale (CSSS-15), Stigma Scale for Chronic Illness (SSCI-8), and treatment adherence (Medical Outcomes Study General Adherence measure; ARMS-7).

PROTOCOL TITLE: *The impact of sharing audio recorded clinic visits on self-management in older adults: a multisite trial*

**Assessments:** A trained RA will collect data (**T0**= Baseline Assessment) by electronic tablet or by paper form if preferred by the patient prior to the visit. Patients who complete eConsent can also complete the baseline assessments via REDCap prior to the clinic visit. The PHQ-8 and GAD-7 will be administered after the clinic visit. Follow up is planned by email (Appendix 25 for the REDCap Survey Template) or telephone at **T1**= one week, **T2**= three months. For T1, the allowable window is up to two weeks from the scheduled timepoint. For T2, the allowable window is up to three weeks from the scheduled timepoint. Deviations from the follow up strategy (e.g., a patient who completes an assessment outside of the planned follow up window) will be reported to the IRB. No participant identifiers will be included on the labeling of study data. Study Unique ID code numbers instead of names will be used on participant materials, data and data-collection instruments to minimize risks regarding breach of confidentiality.

Patients will receive a printed schedule of follow-up assessments, tailored to times and days convenient to them.

Outside of the standard study follow up assessments, the patient will be met in clinic or contacted by email or telephone one week from any scheduled visit with a participating clinician to assess intervention use (AVS or AUDIO) and interpersonal processes of care (IPC) survey (immediately following the clinic visit, or within 1 week of the visit by email or telephone with the RA).

**6.4 Outcomes:** Our primary and exploratory outcome measures are outlined in Section 4.2 Table 1.

**6.4.1 Covariates:** Demographic information (age, sex, race, ethnicity, language used at home, educational attainment using categories from the 2016 American Community Survey) will be collected by the RA through patient report at enrollment. We will document if a caregiver (a support person, family member or friend) is present at the visit. We will collect demographic and practice information about participating clinicians including their age, sex, race, ethnicity and years in practice. The following covariates will be examined in our exploratory moderator analysis:

**Health literacy:** We will use two assessments, the 3-item validated Brief Health Literacy Scale (BHLS) and the 18-item validated Short Assessment of Health Literacy (SAHL-E). Both scales are validated in English and Spanish. Scores on the BHLS range between 3 and 15, with higher scores indicating higher subjective health literacy. Scores on the SAHL-E range from 0 – 18; ≤14 is considered low health literacy

**Disease burden:** The Charlson Comorbidity Index (CCI) using EMR data. Each condition is assigned a score, based on risk of death, which is summed, with higher scores indicating higher disease burden.

PROTOCOL TITLE: *The impact of sharing audio recorded clinic visits on self-management in older adults: a multisite trial*

**Depression:** The eight-item PHQ-8 validated in both English and Spanish. Scores range from 0 – 24; a score  $\geq 10$  indicates major depression, and a score of  $\geq 20$  indicates severe major depression.

**Anxiety:** The seven-item GAD-7 validated in both English and Spanish. Scores of 5, 10, and 15 represent cut points for mild, moderate, and severe anxiety, respectively.

**Diabetes Stigma:** The comprehensive diabetes stigma scale (CSSS-15) is a validated 15-item assessment of diabetes-related stigma. It is composed of four subscales: (1) enacted (0-6), (2) perceived (1-5) and (3) self-stigma(1-5), and (4) concealment (1-5). Subscale scores are means of responses, and an overall score is the sum of all items (11-96).

**Stigma of Chronic Illness.** The Stigma Scale for Chronic Illness (SSCI-8) is validated, eight-item assessment of stigma related to chronic disease. It is scored from 8 (low stigma) to 40 (high stigma), and can be converted on to a standardized T-distribution score with a mean of 50 and standard deviation of 10.

**Audio & AVS Use:** Intervention use by patients will be monitored within the HealthPAL application: we can determine when a 1. patient logs into their account; 2. listens to a recording; and 3. shares the recording. AVS use will be assessed at standard outcomes assessments and one week from scheduled clinic visit during the data collection period: we will determine whether the patient reviewed the AVS and whether they shared it.

**6.8 Debrief interviews (Aim 2):** Upon completion of the data collection for Aim 1, we plan to enroll participants for Aim 2. We will evaluate the acceptability of our study protocol and AUDIO intervention, barriers and facilitators to implementation of audio recordings through semi-structured interviews with patients, caregivers of intervention arm participants (a person who assists with the patient's care e.g. family member, friend) and clinicians at the three study sites: Dartmouth-Hitchcock Primary Care (Manchester, NH and Bedford, NH), Vanderbilt University Medical Center (Nashville, TN), and University of Texas Medical Branch, Internal Medicine - Geriatrics Clinic (Galveston, TX). We will select a sample of trial patient-participants (N=6), caregivers of intervention arm participants (N=6) and clinicians (N=6) at each site, for a total of 54 participants (18 patients, 18 caregivers, and 18 clinicians). In addition to this, we will plan to supplement our interviews with two additional Spanish language patient and caregiver participants at our UTMB site if the participants wish to take part. Given estimates that thematic saturation typically occurs between 12-18 interviews, we expect that our sample size for each stakeholder group (patients, caregivers, clinicians) will be adequate to achieve saturation of key themes.

**Study procedures:** Interview procedures will be similar across the stakeholder groups.

**PROTOCOL TITLE:** *The impact of sharing audio recorded clinic visits on self-management in older adults: a multisite trial*

When permission is granted, interviews (phone calls or in-person) will be conducted in a private area by a Research Assistant trained in qualitative methods and supervised by [name]. Interviews are expected to be 20-30 minutes in duration.

Interviews will be recorded using a digital recording device. These recordings will then be transcribed. When consent for recording is not granted, we will proceed with the interview and take detailed notes. If patients cannot be reached via telephone, an effort will be made to meet the patient at their next scheduled appointment to determine interest in continuing to that part in the project.

## **and Specimen Banking\***

### ***a storage and sharing plan***

The Dartmouth Institute for Health Policy & Clinical Practice has a rich tradition of making final research data available to the public. The posting of all final data from the Dartmouth Atlas of Healthcare is perhaps the best example of this institutional commitment to reinforcing open scientific inquiry, encouraging diversity of analysis and opinion, promoting new research and critical review, and facilitating alternative analyses of datasets used in our published work. In keeping with our institutional policy for collaborating with the broad scientific community in the interest of advancing health and health care, we will publish results from this research work in peer-reviewed medical, economic and health policy journals. We will make analytic code and variable creation and restructuring de-identified information publicly available through the Dartmouth website (<https://dataverse.dartmouth.edu>).

In addition to the study-specific sharing plan outlined above, Dartmouth maintains the following universal data sharing policy for all investigators:

1. Data will be made available, in accordance with the NIH Data Sharing Policy ([http://grants.nih.gov/grants/policy/data\\_sharing](http://grants.nih.gov/grants/policy/data_sharing)) to all researchers in both the private and public sector free or for a nominal charge and with minimal restriction. In some cases the Trustees of Dartmouth College (the institution) may determine that the public and the research community are better served by a licensing program whether or not patents have been filed.
2. So that the entire research community can benefit from the data generated by the institution, pending third parties rights, the institution will transfer materials to outside researchers under Material Transfer Agreements (MTAs) generated and monitored by Dartmouth's Technology Transfer Office. Such MTAs will be made with no more restrictive terms than the Simple Letter Agreement (SLA) to non-profit institutions or the Uniform Biological Material Transfer Agreement (UMBTA) to for-profit ones.

Generally, the MTA will also include a requirement that new data developed by

PROTOCOL TITLE: *The impact of sharing audio recorded clinic visits on self-management in older adults: a multisite trial*  
recipients of the tool becomes a part of publicly available data.

As a means of sharing knowledge, NIH encourages grantees to arrange for publication of NIH-supported original research in primary scientific journals, registered in PubMed Central database of the National Library of Medicine. Awardees therefore will strive to publish their findings in a timely manner and acknowledge that the research was supported by the NIH. Brief delays in publication may be appropriate to permit the filing of patent applications and to ensure that confidential information obtained from industrial collaborator is not inadvertently disclosed. However excessive publication delays, requirements for editorial control or withholding of data undermine the credibility of research results and would be unacceptable to the institution.

## 8.0 Sharing of Results with Subjects\*

We plan to share a summary of results and next steps by email/post to all participants at the completion of data analysis.

## 9.0 Study Timelines\*

Upon Notice of Grant Award (Year)	1				2			
Quarters	1	2	3	4	1	2	3	4
Protocol & Consent Document Development								
DSMB and sIRB Approval								
Protocol Registration on ClinicalTrials.GOV								
Submission & Final Approval of Documents to IRBs								
Data & Safety Management Tasks								
Staff Training (two day kick-off meeting)								
Facility Site Preparation								
Site Activation Checklists Complete								
Recruitment and Enrollment								
Outcome Assessment								
Participant Interviews								
PI site meetings								
DSMB Annual Review								
Data quality checks and cleaning								
Data Analysis								
Dissemination Meeting								
Manuscripts and Reports								
R01 submission								

## 10.0 Inclusion and Exclusion Criteria\*

PROTOCOL TITLE: *The impact of sharing audio recorded clinic visits on self-management in older adults: a multisite trial*

### **10.1 Inclusion / Exclusion criteria (Aim 1 Trial)**

Inclusion criteria (Aim 1): Inclusion criteria will be assessed by the RA by using the EMR to identify potential eligible patients followed by a telephone screening assessment (SA). We will include patients who are (1)  $\geq 65$  years (EMR abstraction); (2) with diabetes and hypertension and receiving medication for each (EMR abstraction); (3) have had one or more clinic visits in the previous seven months (EMR abstraction); and (4) plan on receiving ongoing care at the clinic for the subsequent 6months (SA). By selecting patients who have  $\geq 1$  visits in a seven-month period, we define a population who may require regular management and have a greater opportunity to benefit from visit recordings. We will only include patients of clinicians (MDs, NPs) who (1) are based at the study clinic; (2) who treat adult patients. Clinic leads have presented the project to clinical teams and confirmed willingness of clinicians to take part.

Exclusion criteria (Aim 1): We will exclude patients (1) without capacity to consent to the project (SA) (2) with dementia, schizophrenia and other psychotic disorders, substance-use disorders, uncorrectable hearing or visual impairment (EMR abstraction) or a six item screener (SIS) cognitive function score  $\leq 4$  as this indicates significant cognitive impairment (SA); (3) living in skilled nursing homes or hospice because they engage far less in self-management (SA); (4) patients who have audio- recorded a clinic visit for their personal use in the previous six months (SA); (5) patients who do not have their diabetes and hypertension medication managed by the study clinician; and (6) patients who (a) do not have access to a personal email, (b) do not have an email address shared with a family member or patient-identified caregiver, and/or (c) are not interested in creating an email account between the time they are first contacted by the study team to the time that the study team requires an email address to initiate the online recording software registration. The SIS of cognitive function is validated for use with older adults and highly correlated with Mini-Mental State Exam (MMSE). Study clinicians will be notified in-person, by telephone, or by site-specific secure communication method of any patients with a six item screener (SIS) cognitive function score  $\leq 4$ , in order to alert them of a potentially clinically-significant finding which may require follow up. We will exclude clinicians who (1) are trainees, e.g., medical students or residents; or (2) commonly audio or video record clinic visits for patient's personal use.

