In both instances the patient and clinician can choose to stop or start the recording at any time by indicating this to the RA or stopping the recording device directly (e.g. where RA is outside of the room). The RA will schedule a time to meet with the patient via web conference, by phone or in person separate from the clinic visit, during which the RA will follow standardized instructions demonstrating how to access recordings. Pre- and post-visit surveys will be administered remotely, by email or telephone, for patients having telehealth visits.

The research team will maintain a copy of all recordings locally on a secure, HIPAA

PROTOCOL TITLE: *The impact of sharing audio recorded clinic visits on self-management in older adults: a multisite trial*

compliant server, captured by a second recorder, which will also serve as a back-up; once transferred to the server, the recording will be deleted from the digital recorder. Patient **access to recordings** will be possible via a secure web-based platform: HealthPAL.

HealthPAL. All patients with access to email will be able to access their recording online. The recording and sharing of the recorded data will be facilitated via HealthPAL, an online platform developed by PI [name] at Dartmouth (Appendix 4. HealthPAL system). The RA will register the patient in the HealthPAL system. Within the system they can record visits, which can then be accessed later online at home. The RA will demonstrate how to access and playback the recording on a computer or smartphone using each patient's unique login information. Access details (web address, login and use instructions) will be shared with patients both by email and on paper.

HealthPAL is a web application that runs on Amazon's cloud infrastructure (AWS). The root account under which the application is hosted is owned by Dartmouth College, which has a Business Associates Agreement (available upon request) in place with Amazon for the use of Amazon's HIPAA-eligible cloud services with Protected Health Information. All cloud services used by HealthPAL are covered under this agreement (Appendix. 5 HealthPAL security document).

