project coordinator at Dartmouth College will prepare and send recruitment materials to each site prior to the beginning of data collection and will prepare the randomization sequence in REDCap. Upon completion of pre-visit baseline assessment (T0), the RA at the study site will reveal the participants group allocation using the randomization feature in REDCap. Patients will be offered an AVS per the usual practice at their clinic, either on paper or via patient portal, but only patients in the AUDIO arm will receive access to audio recordings from the RA to review online at home. The randomization process will be operationalized and supervised by study statistician (Co-I [name]).

**Study procedures:** All participating patients and clinicians will provide informed consent. Clinicians will proceed to complete a brief demographic survey. Patients will proceed to complete the pre-visit baseline assessment surveys. The baseline assessment will be administered in a private area of the waiting room in the clinic, private research office, or an available exam room. Patients will also have the option to complete baseline assessment online in REDCap or over the phone with research staff prior to the clinic visit if they opt for eConsent. We have piloted the administration of the patient surveys with older adults aged 65 or older and estimate that completion will take 20 minutes. After completing the pre-visit baseline assessment, patients will be randomly allocated to AUDIO or UC alone, and informed of which group they have been assigned to. If patients are unable to complete pre-visit surveys prior to meeting with the clinician due to time constraints, the surveys may be completed after the visit. Patients meeting the clinician in person will then be escorted by the RA to the vital sign area to meet a medical assistant and/or back to the waiting room.

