to collect data during a two-day 'kick-off' training session prior to patient recruitment. Study data will be directly inputted to electronic surveys using REDCap, providing an opportunity to prevent and monitor missing data. At recruitment, the RA will ask patients for an email and phone number to conduct follow-up assessments (by email and/or telephone calls), and to provide contact details for another person if they cannot be reached for follow-up. Follow-up contact attempts may be made by telephone, email, or post, but will be limited to no more than one attempt per day, for up to two weeks from planned T1 assessment, and three weeks from planned T2 assessment. Patients who cannot be reached by telephone will be approached in the clinic to determine their desire to remain in the study and complete follow-up assessments. or document reason for withdrawal if they do not wish to remain. All attempts to contact patients will be documented in REDCap. We will also conduct weekly workbench reports from the EMR to confirm scheduled visits of recruited patients during the follow-up period.

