## **14.0 Withdrawal of Subjects\***

Any participant can discontinue participation at any time. An investigator may also discontinue or withdraw a participant from the study for the following reasons: 1) disease progression which requires discontinuation of the study intervention, or 2) if the participant meets an exclusion criterion (either newly developed or not previously recognized) that precludes further study participation. The reason for participant discontinuation or withdrawal from the study in either case will be recorded on the Participant Withdrawal Case Report Form (Appendix 15. Participant Withdrawal Form).

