#### 17.1.2 Acceptability (Aim 1.2)

Assessing the proportion of patients and clinicians who agree to take part in the project and proportion of patients who listen to the recording (we will target >70%). Our primary indicator of acceptability will be the recruitment of 108 participants (n=30 patients and 6 clinicians per site) over our planned data collection period of six months. We will determine the listening rates (we will target >70%): this will include the proportion of patients in the intervention arm that log in to the online system and listen to (and how often) the recording. We will also document the number of patients who share or report sharing the recording and caregivers who access the recording. Finally, participants will complete the Acceptability of Intervention Measure (4 items; target an average score of >3). If we fall short of targeted thresholds, we will determine the need for deviations from the existing study protocol. We will contact participants who do not adhere to the listening regime, outside of the standard follow-up assessments to determine if changes are required to the intervention delivery.

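### The email exclusion stays open until HealthPAL registration, a step described only for AUDIO, so a patient without email could be excluded after allocation in one arm only

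*Combined protocol and SAP*

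**What the plan says.** Section 10.1 ties most patient exclusions to a source: the electronic record or the telephone screen. Exclusion (6), on email, has no such tag. It has its own window, running from first contact "to the time that the study team requires an email address to initiate the online recording software registration". Its limbs are joined loosely: "do not have an email address shared with a family member or patient-identified caregiver, and/or (c".

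Registration appears in the HealthPAL text of section 5.2, the Audio Intervention: "The RA will register the patient in the HealthPAL system". No step in the protocol registers UC patients. Section 5.1.2 says UC patients have no further clinic procedures after baseline, apart from an optional survey at later visits.

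Section 6.1 sets the time of allocation: "Upon completion of pre-visit baseline assessment (T0), the RA at the study site will reveal the participants group allocation". It adds that "only patients in the AUDIO arm will receive access to audio recordings from the RA to review online at home".

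Section 14.0 lets an investigator withdraw a participant "if the participant meets an exclusion criterion (either newly developed or not previously recognized) that precludes further study participation".

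Section 6.2 asks both arms for an email, but for follow-up: "At recruitment, the RA will ask patients for an email and phone number to conduct follow-up assessments (by email and/or telephone calls").

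Sections 4.1 and 17.1.2 set a listening target of >70%, defined as the "proportion of patients in the intervention arm that log in to the online system and listen to (and how often) the recording".

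**The concern.** Eligibility should be fixed before allocation and by the same test in both arms. Here the event that closes exclusion (6) is a step of the AUDIO intervention. A patient without email who is allocated to UC never reaches that step. The same patient allocated to AUDIO does reach it, and section 14.0 then offers a route out of the trial.

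Two things would be at stake. First, patients without email are plausibly among the least able to use an online recording. Removing them from one arm only would disturb the as-randomized comparison on the Patient Activation Measure and the health-literacy question. It would also lower the share of AUDIO patients reporting no recording, which section 17.1.4 uses to estimate refusers. Second, a patient who cannot be registered cannot listen. Dropping that patient from the denominator raises the listening rate, which is part of the primary acceptability endpoint. No analysis set is defined, and nothing says how a patient excluded after allocation is counted.

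**Working it through.** **Order of events.** Telephone screen (13.1); for in-person consent, criteria confirmed again and then consent (22.1.1); pre-visit baseline; allocation revealed (6.1); AUDIO visit recorded (5.2 and section 6.0, study procedures). Registration is described with recording and access, so the natural place for it is after allocation and in AUDIO only. The protocol does not state either point; both are inferred from where the step sits.

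**The plan's own total.** Three sites × (30 patients + 6 clinicians) = 108, and 3 × 30 = 90 patients, as section 26.0 states. With 1:1 allocation, the expected AUDIO arm is 90/2 = 45.

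**Listeners needed.** Take the smallest x with x/m > 0.70, where m = 45 − k and k is the number of allocated AUDIO patients excluded late for email and dropped from the denominator. The documents give no k; I assume 0 to 5, with every dropped patient a non-listener.

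| k | Denominator | Listeners needed | Reported rate | Same count over 45 |
|---|---|---|---|---|
| 0 | 45 | 32 | 71.1% | 71.1% |
| 1 | 44 | 31 | 70.5% | 68.9% |
| 3 | 42 | 30 | 71.4% | 66.7% |
| 5 | 40 | 29 | 72.5% | 64.4% |

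Dropping k patients multiplies the reported rate by 45/(45 − k): 1.02, 1.07 and 1.125 for k = 1, 3 and 5.

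**Chance of meeting the target.** Suppose, for illustration, that the true rate among all allocated AUDIO patients is 65%. After k non-listeners are dropped, the rate among the rest is 0.65 × 45/(45 − k). The binomial probability of reaching the needed count is 24% for k = 0, 35% for k = 1, 48% for k = 3 and about 61% for k = 5.

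**Arm size.** Thirty patients over 6 clinicians averages 5 each, an odd number for blocks of 2. With exactly 5 per clinician, each contributes 2 or 3 AUDIO patients, so the arm could be 18 × 2 = 36 to 18 × 3 = 54.

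- At 36, one dropped patient is enough to matter: 25/36 = 69.4% misses, 25/35 = 71.4% meets.
- At 54, it takes two: 37/54 = 68.5% and 37/53 = 69.8% miss, 37/52 = 71.2% meets.

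**The case against.** The strongest reply is that the criterion tests interest, not success. Limb (c) covers patients who do not want to create an account. Someone who agrees on the telephone to set one up is interested, and on the wording does not clearly meet (c) merely because no account exists at registration. This stands. The clear route to late exclusion is a patient who loses interest within the window. A willing patient who never creates an account has no defined status.

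Second, eligibility is screened by telephone and, for in-person consent, confirmed again before consent, and both arms are asked for an email at recruitment. For most patients the question could well be settled before allocation, and patients using eConsent already receive a REDCap link by email. But these checks do not close the window. The criterion by its own terms is not yet due when they are made, and the email request serves follow-up that may be done by telephone instead.

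Third, a reader might infer from all this that the listening rate *is* inflated. The documents do not support that. The stated denominator, read literally, keeps every allocated AUDIO patient. Section 14.0 permits withdrawal but removes nobody from a denominator. Inflation needs both a late exclusion and an unstated rule that drops the patient. The counts of 31 and 30 were also chosen because they lie close to the threshold.

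Fourth, the consequences are limited. The protocol names recruitment of 108 as its primary indicator of acceptability, the activation outcome is exploratory and unpowered, and missing the listening target only prompts consideration of protocol changes. That is fair and limits the weight of the point.

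Finally, the and/or wording could be read as excluding a patient who has a personal email but no shared one. This conflicts with section 5.2, which offers online access to all patients with email. The intent is evidently that all limbs must hold, so this is drafting and not evidence of bias.

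**Conclusion.** The point holds as a gap in the rules. Exclusion (6) has no cut-off before allocation, the event that closes it is described only for AUDIO, and late withdrawal for an exclusion criterion is allowed. Together these permit an exclusion after allocation that depends on arm. That registration follows allocation and is confined to AUDIO is the natural reading, not explicit text.

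The effect on the listening rate is conditional. With an expected 45 in AUDIO, a single dropped patient can turn a miss into a pass, but only if a late exclusion occurs and the patient leaves the denominator. With no late exclusions, or with all allocated patients counted, there is no inflation. The number of such patients is not documented, so neither the listening rate nor the between-arm comparison can be said to be biased on this evidence. The change is still worth making, because it is cheap and removes the possibility.

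**What to change.** 1. Reword exclusion (6) so that a patient is excluded only if (a), (b) and (c) all hold: no personal email, no shared family or caregiver email, and no interest in creating one.
2. Settle the criterion, and record a usable personal or shared email, for every patient in both arms before the REDCap allocation is revealed. The deadline should be the reveal itself and not the end of T0: the baseline assessment includes items given after the visit, and pre-visit surveys may also be completed afterwards.
3. After allocation, do not use lack of email as an exclusion. The patient stays in the assigned arm.
4. State that the listening denominator is every patient allocated to AUDIO, with those who have no access counted as non-listeners. Report any email exclusion made after allocation, by arm.

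The cost is one reworded criterion, one REDCap field completed before the reveal and one sentence in section 17.1.2. The small downside is that a few in-person patients must set up an email before allocation or be screened out earlier. If recruitment has already finished, step 4 can still be applied at analysis.
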